13 E-DIARIES

Subjects will be instructed to complete e-diaries daily. Training and detailed instructions on how to complete the e-diary will be provided to subjects. The screening period will be used to train the subjects on how to use the e-diary and to assess the subject's e-diary completion compliance. The diary data collected during the screening period will not be used in the analysis. Subjects will have up to 7 days to input e-diary data for each day. During subject visits and contacts, the site should review the e-diary with the subject to assess for e-diary completion. In addition, all e-diary entries should be reviewed and assessed for adverse

events and concomitant medications. Subjects should be re-educated if they are not completing the diary or are incorrectly completing it. E-diaries are designed to collect the following information for each day of the 28-day cycle from Screening through Month 12:

- Day of cycle
- Date
- Absence or presence of scheduled (menstrual) or unscheduled (intermenstrual)
 vaginal bleeding/spotting (none, spotting, light bleeding, normal bleeding or heavy
 bleeding)
- Vaginal intercourse
- IUD expulsion (yes, no, suspected)
- Usage of additional birth control methods and type of birth control used
- Presence of menstrual pain or cramping
- Adverse events
- Concomitant medications

Vaginal bleeding categories are defined as follows:

- None: no bleeding or spotting
- Spotting: a minimal amount of vaginal bleeding and only one panty liner is used all day or did not use any protection (panty liner, pad, tampon)
- Light bleeding: have vaginal bleeding and one or two pads or tampons are used, or more than one panty liner is used, throughout the day
- Medium bleeding: have vaginal bleeding and three or four pads or tampons are used throughout the day
- Heavy bleeding: have a large amount of vaginal bleeding and more than four pads or tampons are used throughout the day

From Month 13 – Month 96 the following will be collected:

- Day of cycle
- Date
- Vaginal intercourse
- IUD expulsion (yes, no, suspected)
- Usage of additional birth control methods and type of birth control used
- Adverse events
- Concomitant medications

14 CONCOMITANT MEDICATIONS AND DEVICES

Concomitant medications include any medication (any prescription medications or over the counter preparations) taken from the time the subject signs the informed consent/assent

documents until VeraCept removal/ expulsion or medications used to treat reportable SAEs occurring after study drug removal and must be recorded appropriately on the eCRF. In addition, concomitant medications used as prior contraception or used to treat a prior cervical infection within 30 days of informed consent/assent should also be reported.

14.1 Prohibited Concomitant Medications

- The use of misoprostol prior to the study IUS insertion is not recommended except where needed, at the discretion of the Investigator [11].
- The use of contraceptive or non-contraceptive estrogen, progesterone, testosterone or gonadotropin (e.g., hCG) is not allowed during the study.
- Medications that require the use of double barrier contraception (e.g., Isotretinoin brand names Absorica®, Accutane®, Amnesteem®, Claravis®, Myorisan®, Sotret®, and ZenataneTM).
- Any other birth control method that could potentially affect the results of this study should not be used during study participation. However, if the subject believes she will be at risk for an STD, then she should use a condom for protection.
- Any other investigational treatment or medication other than VeraCept, unless approved by the sponsor.
- Subjects who begin to chronically use excluded therapies or illegal drugs may be discontinued from the study. Investigators must contact the Medical Monitor to discuss possible discontinuation of these subjects.
- Subjects should be instructed to abstain from using menstrual cups and discs to avoid accidental IUS removal during menstrual cup and disc removal. Menstrual cup and disc use may dramatically increase the likelihood of unintentional IUS expulsion and should not be used. If a subject cannot be discouraged from using a menstrual cup or disc, ensure the subject is familiar with the menstrual cup and disc instructions for use for proper insertion and removal. It is recommended that placement be low in the vagina and not in contact with the cervix. Should a menstrual cup or disc user notice that the cup or disc is in contact with the cervix the recommendation is to pinch the edge of the cup or disc first to break the seal of the cup or to avoid pulling the IUD strings that may be in contact with the disc and then removing the cup or disc.

15 ADVERSE EVENTS AND SERIOUS ADVERSE EVENTS

During the study, the investigator or study site personnel will be responsible for querying and recording adverse events (AEs) and serious adverse events (SAEs), as detailed below. For the sponsor to fulfill safety assessment obligations, the investigator must report all SAEs to the study sponsor, whether or not they result from study participation, within 24 hours of learning of the event.

15.1 Definition of a Serious Adverse Event

A serious adverse event (SAE) is any adverse event occurring within the timelines specified in the protocol that results in any of the following outcomes:

- Death;
- Life-threatening situation (subject is at immediate risk of death);
- Inpatient hospitalization or prolongation of existing hospitalization;
- Persistent or significant disability/incapacity;
- Congenital anomaly/birth defect in the offspring of a subject who received study drug; or
- Important medical events that may not result in death, be immediately life-threatening, or require hospitalization, may be considered an SAE when, based upon appropriate medical judgment, they may jeopardize the subject and may require medical or surgical intervention to prevent one of the outcomes listed in this definition. Examples of serious adverse events include but are not limited to: intensive treatment in an emergency room, hospitalization for any reason, and extensive treatment at home for an adverse event. An ectopic pregnancy is considered a serious adverse event.

15.2 Definition of an Adverse Event

An adverse event is any untoward medical occurrence in a clinical investigation subject administered an investigational product and which does not necessarily have to have a causal relationship with this treatment. An AE can, therefore, be any unfavorable and unintended sign (that could include a clinically significant abnormal laboratory finding), symptom, or disease temporally associated with the use of a medicinal product, whether or not considered related to the medicinal product.

Any AE (i.e., a new event or an exacerbation of a pre-existing condition) with an onset from the day of informed consent/assent through VeraCept removal or expulsion should be recorded as an AE on the eCRF. An event that is discovered during the screening visit that clearly started or was acquired prior to obtaining informed consent (e.g., positive cervical infection test, positive cervical pathology) should be recorded as medical history and not as an AE. All AEs must be recorded regardless of the severity or relationship to study drug. It is important that investigators also report all AEs that result in expulsion or removal of the investigational product being studied, whether serious or non-serious.

Pregnancy is an outcome, and not an AE in this study.

15.3 Adverse Events of Special Interest

Adverse events of particular clinical importance, other than SAEs will be classified as adverse events of special interest (AESIs). For this study, AESIs refer to reports of pain during insertion, pelvic infection (PID or endometritis), dysmenorrhea, abdominal pain, expulsion and uterine perforation. AESIs will be identified and assessed by the Medical

Monitor during the ongoing monitoring of safety data during the trial, during DMSB

meetings and for the Clinical Study Report. For each AESI, a narrative may be written and included in the Clinical Study Report.

15.4 Causality: Serious Adverse Event and Adverse Event Relationship to Study Treatment

An Investigator who is qualified in medicine must make the determination of relationship to the drug for each AE. The relationship of an AE to the drug should be assessed using the guidelines presented in Table 2. An AE for which there has been no causal relationship reported initially will require follow-up to determine causality. Of the definitions in Table 2, "possibly", "probably" and "related" to an investigational medical product are considered adverse reactions. "Unlikely" and "not related" do not qualify as a causal relationship.

Table 2: Adverse Event Relationship to Drug

| Relationship to Drug | Description | |
|-------------------------|--|--|
| Related | Previously known toxicity of agent; or an event that follows a reasonable temporal sequence from administration of the drug; that follows a known or expected response pattern to the suspected drug; that is confirmed by stopping or reducing the dosage of the drug; and that is not explained by any other reasonable hypothesis | |
| Probably related | related The adverse event: | |
| | • Follows a reasonable temporal sequence from the time of study drug administration; and/or | |
| | Follows a known response pattern to the study drug; and | |
| | Was unlikely to have been produced by other factors such as the subject's clinical state, therapeutic intervention, or concomitant therapy | |
| Possibly related | The adverse event: | |
| | • Follows a reasonable temporal sequence from the time of study drug administration; and/or | |
| | Follows a known response pattern to the study drug; but | |
| | Could have been produced by other factors such as the subject's clinical state, therapeutic intervention, or concomitant therapy | |
| Unlikely related | The adverse event: | |
| • | • Does not follow a reasonable temporal sequence from the time of study drug administration; and | |
| | Was likely produced by other factors such as the subject's clinical state, therapeutic intervention, or concomitant therapy but for which relationship cannot be definitely ruled out | |
| Not related | The adverse event can be determined with certainty to have no relationship to the study drug | |

15.4.1 Clarification of Adverse Events Related to Study Procedures

Any untoward event that occurs from the time of informed consent/assent, including the study drug placement procedure until completion of placement, or from the beginning of the removal procedure until the completion of removal, will be reported as an AE. The AE

should be recorded on the AE eCRF with a causality assessment of "related to study drug placement procedure." If the AE also meets the criteria for an SAE, an SAE report should be completed and submitted to the sponsor.

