20.7.3 Safety and Tolerability

The following safety and tolerability analyses will be performed:

- Incidence of AEs and SAEs will be summarized for the ITT population as well as for the Safety populations for all subjects and the 36 to 45-year-old safety subpopulation. The number and percentage of subjects with each AE and SAE will be presented in a table by MedDRA system-organ class and preferred term. Summaries will be presented by relationship to VeraCept and/or VeraCept placement or removal procedure and the severity of the adverse event. All AEs will be summarized, including these AESIs:
 - Pain during insertion
 - Pelvic infection (PID or endometritis)
 - Expulsion
 - Uterine perforation
 - Dysmenorrhea
 - Abdominal pain
- Bleeding and spotting patterns will be summarized (per Mishell [12]) for the ECYC population for the first year of treatment by the number of days in each 28-day cycle with bleeding or spotting, bleeding only and spotting only.
- The insertion pain assessed immediately after insertion will be summarized...
- Cumulative VeraCept continuation rates for Years 1 through 8 will be summarized using Kaplan-Meier methods for the Safety population. The number and percentage of subjects with each reason for discontinuation will be summarized.
- Cumulative VeraCept expulsion rates at for Years 1 through 8 will be summarized using Kaplan-Meier methods for the Safety population.

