4.1.10.5 Adverse Events Related to Study Procedures

Adverse events that occur during the study drug placement procedure or removal procedure will be reported on the AE electronic case report form (eCRF) with a causality assessment of "related to study drug placement procedure."

A missing relationship will be imputed as "related to study drug placement procedure."

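### Protocol 15.4.1 and SAP 4.1.10.5 give removal events, and under the Protocol all events from consent to placement, a placement-procedure causality label, which records wrong procedural causality and leaves placement and removal risk unseparated in the planned AE tables

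*Protocol*

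**What the plan says.** Protocol 15.2 collects AEs from the day of consent to removal or expulsion. Only conditions that clearly began before consent go to medical history. Protocol 15.4 has an investigator grade every AE against the drug: "The relationship of an AE to the drug should be assessed using the guidelines presented in Table 2".

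Protocol 15.4.1 adds a procedural rule with two windows. The first is "Any untoward event that occurs from the time of informed consent/assent, including the study drug placement procedure until completion of placement". The second runs "or from the beginning of the removal procedure until the completion of removal, will be reported as an AE". An event in either window "should be recorded on the AE eCRF with a causality assessment of" being related to the placement procedure. There is no label for removal, and no option for an event that has nothing to do with either procedure. If the event is serious, the same section asks for an SAE report.

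SAP 4.1.10.5 states the rule differently: "Adverse events that occur during the study drug placement procedure or removal procedure will be reported on the AE electronic case report form", again with the placement label. It continues "A missing relationship will be imputed as" that same label, and states no limit by date of onset.

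For reporting, Protocol 20.7.3 says "Summaries will be presented by relationship to VeraCept and/or VeraCept placement or removal procedure". SAP 4.12.1 and 4.12.2 use one pooled placement/removal category, and SAP 4.12.4 plans a pooled listing. SAP 4.12 restricts AE summaries to treatment-emergent events, which SAP 4.1.10.1 defines by the first treatment date.

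**The concern.** The Protocol rule settles procedural causality by when an event happened, not by what caused it. Consent can precede insertion, so a cold or a sprain in between is, on the literal text, recorded as caused by the placement procedure. A complication of removal, up to 8 years later, gets the same label. The SAP repeats the removal error and adds an imputation that can give the placement label to an AE far from any procedure.

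What is at stake is the account of procedural risk. Insertion and removal are separate decisions for a user, and removal has hazards of its own in these documents. Protocol Appendix 5 mentions pain, bleeding, vasovagal reactions, seizure, difficult removals that may need hysteroscopy, and devices that are not intact. Protocol 6.2 mentions embedment that may need surgical removal. A record that calls all of this placement-related, and tables that pool the two procedures, do not tell a reader which procedure carries which risk.

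**Working it through.** The plan states no figure on this point, so the check sets the sections side by side and follows five kinds of event through them.

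| Event | Protocol 15.4.1 | SAP 4.1.10.5 | Where the label shows |
|---|---|---|---|
| Unrelated illness on a day between consent and the first insertion attempt | Placement label | Outside the window | eCRF, any SAE report, listing of non-treatment-emergent events; not the AE tables |
| Unrelated event on the day of insertion, before the procedure | Placement label | Outside the window | eCRF, listings and procedure-related tables |
| Unrelated event between a failed first attempt and a second attempt | Placement label | Outside the window | eCRF and listings; possibly the tables |
| Complication during removal | Placement label | Placement label | eCRF, any SAE report, listings; in the tables only inside the pooled category |
| AE long after insertion with a blank procedure relationship | No rule | Placement label imputed | Procedure-related tables |

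1. **Between consent and insertion.** SAP 4.12 limits summaries to treatment-emergent events and SAP 4.12.4 lists the others separately. The wrong attribution therefore stays in the record and the listings.

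2. **Same day.** Treatment emergence is decided by date, and the note to Protocol Table 1 allows screening and enrollment to be combined. An event that morning, before the procedure, counts as treatment-emergent and carries the label.

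3. **Two attempts.** Protocol 12.3 allows a second attempt on the same day or within 1 week. Until it succeeds, placement is not complete, so 15.4.1 still applies. SAP 4.1.2 dates ITT analyses from the first attempt. SAP 4.1.10.1 does not say whether the first treatment date means the first attempt or the successful one, so entry to the tables is possible but not certain.

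4. **Removal.** Both documents give the placement label. In the pooled category of SAP 4.12.1 and 4.12.2 the event is counted where it belongs, so the pooled total is right. The record of which procedure was responsible is wrong.

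5. **Blank relationship.** SAP 4.1.10.4 imputes a missing drug relationship for any AE. SAP 4.1.10.5 uses the same form of words for the procedure relationship, also with no onset limit. Protocol 15.4 instead calls for follow-up when no causal relationship was reported initially, although it speaks there of relationship to the drug.

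6. **Can the two procedures be separated?** SAP 4.12.4 lists AE onset relative to first insertion, and SAP 4.1.5 derives the study day of removal. The dates needed for a split exist. The label does not make the split, and neither do the tables in SAP 4.12.1 and 4.12.2.

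The SAP was written for protocol version 3.0 and the current Protocol is version 7.0. That may explain why the windows differ. It does not explain the placement label on removal events, which both documents contain.

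**The case against.** The strongest reply is that this is loose drafting with little effect on results. Several parts of it stand.

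- **Drug causality is untouched.** Protocol 15.4 governs relationship to the drug, and the SAP reports drug and procedure relationships as separate items. A reader might infer that the rule overrides the investigator's Table 2 assessment; the documents do not support that.
- **Screening illnesses mostly stay out of the tables**, through the SAP's narrower window and the treatment-emergent filter.
- **The information is not lost.** A reader might infer that insertion risk cannot be told apart from removal risk. That is too strong: onset and removal dates allow a split, and SAP 4.10.2.1 and 4.10.2.2 already report placement and removal ease and pain separately.
- **No placement-only rate is inflated.** A reader might multiply the expected removals by an assumed event rate and call the result an excess in the placement-related rate. No planned table reports such a rate, the event rate would be invented, and expulsions, losses to follow-up and outside or refused removals reduce the number of on-study removals.

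Two further arguments stand only in part. The phrase closest relationship in SAP 4.12.2 suggests that procedural causality is graded in practice, but 15.4.1 leaves no grade to choose. The imputation sentence sits in a section about procedures, so a limited reading is available; it is not stated, and the parallel sentence in SAP 4.1.10.4 points the other way. A merged column can be reconciled with Protocol 20.7.3, but a placement-only label cannot supply the removal relationship named there.

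**Conclusion.** The point holds as a defect in the recording and reporting of procedural causality. On the text as written, unrelated pre-insertion events and removal complications are recorded as placement-related in the eCRF, SAE records and listings. The procedure-related tables are exposed at three narrower places: same-day events before the procedure, possibly events between two attempts, and late AEs with a blank field. Placement and removal risk are not separated by the label or by any planned AE relationship table.

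The number of records cannot be derived, because the documents give no rate of screening events, removal events or blank fields. The first two routes into the tables are likely to be small. The third depends on how well sites complete the field, and site queries should keep it low. The primary endpoint is not involved.

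The conclusion assumes that sites follow 15.4.1 literally and that the imputation applies to every AE with a blank procedure relationship. If either rule is read more narrowly in practice, fewer records are wrong, but the two documents still disagree on the window and still have no removal label.

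**What to change.** 1. Align Protocol 15.4.1 with the SAP, so that the automatic procedural label covers only events with onset during the placement or removal procedure. Let the investigator assess procedural causality for all other events.
2. In both documents, record events during removal as related to the removal procedure.
3. In SAP 4.1.10.5, query missing procedure relationships first. Limit imputation to AEs with onset on the day of a placement attempt or a removal, and assign them to that procedure.
4. In SAP 4.12.1 and 4.12.2, show placement-related and removal-related AEs in separate rows or columns. Recode existing records by comparing onset with the insertion and removal dates.

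The cost is minor rewording, one recode and one table split. Dates cannot restore procedural-causality judgements that were never made, so affected pre-insertion records also need a query to the site.

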15.5 Serious Adverse Event and Adverse Event Severity

The investigator will assess the severity of the AE using the following general guidelines:

Mild: An AE that is usually transient, requiring no special treatment, and does not interfere with the subject's daily activities.

Moderate: An AE that introduces a low level of inconvenience or concern to the subject and may interfere with daily activities but is usually ameliorated by simple therapeutic measures.

Severe: An AE that interrupts a subject's usually daily activity and typically requires systemic drug therapy or other treatment (a severe AE may not necessarily qualify as an SAE).

Life-threatening: An AE that put the subject at immediate risk of death from the event as it occurred. This does not include an event that might have led to death if it had occurred with greater severity.

Fatal: An AE that was the cause of the subject's death.

15.6 Adverse Event Outcome

The investigator will categorize the outcome of each SAE and AE according to the definitions below:

Resolved: The subject recovered from the SAE or AE.

Resolved with sequelae: a condition whereby the consequences of a disease or injury include lingering effects.

Not Recovered/Not Resolved: At the time of the last assessment, the event is ongoing. Note: Ongoing SAEs and AEs are not considered resolved as a result of death and no SAE or AE stop date should be recorded for an AE that is ongoing at the time of death.

Fatal: Adverse Event directly caused death. The sponsor may request that the investigator perform or arrange for the conduct of supplemental measurements and/or evaluations. If a subject dies during participation in the study or during a recognized follow-up period, the sponsor should be provided with a copy of any post-mortem findings, including histopathology. Note: Death is an outcome of an adverse event and not an adverse event in itself. All reports of subject death should include an adverse event term (other than "Death") for the cause of the death.

Unknown: The Adverse Event outcome is unknown due to the subject becoming lost to follow-up or the subject withdraws consent and is unwilling to provide outcome

information. The outcome of "Unknown" should not be used if the subject is still active in study and/or is willing to provide outcome information.

Since reporting of an SAE is required within 24 hours of discovery, Death can be reported as an initial event term and updated to the final diagnosis in a follow-up report. If an adverse event term is not provided, the investigator will be queried to obtain the cause of death. Only in the rare occurrence that no verbatim description of an adverse event can be obtained from the investigative site will "Death – Unknown Cause" be used as the event term.

The investigator should attempt to establish a diagnosis of the event based on the signs, symptoms and/or other clinical information. In such cases, the diagnosis should be documented as the AE (and SAE if serious) and not the individual signs/symptoms.

In the case of abnormal labs or diagnostic tests judged to be clinically significant by the investigator a diagnosis, if known, or clinical signs or symptoms if the diagnosis is unknown, rather than the clinically significant laboratory finding or abnormal assessment, should be used to complete the AE or SAE report. If no diagnosis is known and clinical signs or symptoms are not present, then the abnormal finding should be recorded on the AE or SAE report. If an SAE report is completed, pertinent laboratory data should be recorded on the SAE report, preferably with baseline values and copies of laboratory reports.

